6.3 Assessment of Motor Function and Disability

Children will be assessed by a paediatric physiotherapist:

• Full neurological assessment

- Classification of severity of cerebral palsy using the Gross Motor Classification System.
- Assessment of motor ability using the Movement ABC-2 test in mobile children. The test contains 8 tasks. The tasks cover the following 3 areas: Manual Dexterity, Ball Skills, Static and Dynamic Balance
- Head circumference, height and weight
- Clinical history (including any other identified disabilities such as hearing loss, epilepsy, feeding difficulties, subsequent neurosurgical procedures)

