After initial feasibility testing showed DRIFT was technically possible and promising, the DRIFT randomised trial started recruiting in 2003. Eligible babies were preterm, had an IVH and expanded the cerebral ventricles over pre-determined limits. With parental consent, 74 babies were randomised in Bristol and Katowice, Poland to either DRIFT or to standard therapy which consisted of non-surgical conventional management (lumbar punctures to control excessive expansion and pressure symptoms). If repeated lumbar punctures were needed, a ventricular reservoir was inserted to facilitate tapping CSF.

Short term outcomes in the DRIFT trial showed no difference in shunt surgery or death. There was a significant increase in secondary bleeding in the DRIFT group. Magnetic resonance (MR) imaging was carried out on clinical indications in 36 of the 50 Bristol survivors.

At 2 years post term, severe disability or death was significantly reduced in the DRIFT group, when neurodevelopment was assessed by "blinded" observers [2]. There was an important decrease in severe cognitive disability (Bayley mental development index 3 SDs below mean) from 59% to 31% (adjusted odds ratio: 0.17 [95% CI 0.05-0.57]) and the difference in median MDI was more than 18 points. Developmental quotient at 2 years correlated significantly with qualitative grading of MR brain images at term. Sensorimotor disability remained substantial at 2 years: overall, 48% were unable to walk, and 20% were unable to communicate. Ventricular enlargement is typically greatest in the occipital areas and 9% of the children had no useful vision. Severe sensorimotor disability was less common in the DRIFT group but without reaching statistical significance.

However, while (relatively) short term neurodevelopmental measures are essential in the initial management of perinatal interventions, longer term measures provide far greater validity in assessing long term functioning (and the medical, societal and financial implications of these).

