4. AIMS AND OBJECTIVES

Our primary hypothesis is that neurosurgical drainage, irrigation, and fibrinolytic therapy (DRIFT), which aims to lower pressure, distortion, free iron, and cytokines, will reduce severe cognitive disability in children assessed at school age.

Our secondary hypotheses are that DRIFT will improve:

- (a) cerebral visual dysfunction
- (b) sensorimotor ability
- (c) functional status
- (d) emotional/behavioural difficulties
- (e) preference based measures of health related quality of life
- (f) and reduce the health, social care and broader societal costs at age 11.

The aims of this study:

- 1) To compare cognitive function, visual function, sensorimotor ability and emotional wellbeing, between the two treatment groups in the DRIFT trial at school age.
- 2) To quantify functional status and use of community and specialist health and educational services.
- 3) To estimate the economic cost and outcomes of the DRIFT intervention by age 11, and model long-term costs and outcomes.
- 4) To quantify degree of ventricular dilatation and neurosurgical sequelae in the two treatment groups by clinical neuroimaging.

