7.4 Data Analysis

Analysis will be performed by intention to treat and hence primary outcome (cognitive score) will be assessed by comparing mean scores, and analysed using the Student t-test (unpaired). Developmental Quotient derived from age equivalent cognitive scores will be used as a continuous variable, derived from either the BAS III or BSID Bayley III scales.

For the secondary outcomes with continuous outcomes (eg Movement ABC), these will also be analysed using Students t-test, unless found in this population to not follow a normal distribution, in which case either a suitable transformations will be sought or a non-parametric approach considered.

For the binary secondary outcomes (eg functional motor impairment, Strengths and Difficulties, use of specialised health, rehabilitative or educational services) the Chi-Square or 2-tailed Fishers exact test will be used. Output from the clinical neuroimaging will be transformed into either binary (in the case of radiology reports) or continuous data (in the case of quantitative measures) and analysed as above.

Any sensitivity analyses will be performed using multivariate linear regression analysis to control for variables of interest. Co-variate variable selection will be performed a-priori for the models, and included if clinically felt to represent potentially important cofounders. To provide consistent reporting, it is anticipated that at least one sensitivity analysis will be performed: adjusting for the pre-randomisation co-variates used in the initial DRIFT trial report.

For all tests a conventional level of statistical significance at 5% will be used.

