10.2 Other Ethical Considerations

Children as participants:

Parents will be asked to consent on behalf of their child. The children will also be asked to provide assent to take part.

Risks, burdens and benefits:

There is no risk to participants in the study. Extensive research has been conducted into whether the magnetic and radio waves that are used in MRI could pose a risk to the human body. No evidence that there is a risk has ever been found. This means that MRI is one of the safest medical procedures currently available.

There is no direct benefit to children enrolled in the study. There are potential benefits to the paediatric population as a whole (i.e. infants affected by the same disease in the future), in terms of increased knowledge of the condition, which would possibly translate into better/earlier diagnosis, treatment or prevention.

Where parents have indicated that children have severe mobility or emotional problems and travel to CRICBristol for assessments would be difficult the study team will be prepared to travel to perform the assessments at home or the school, whichever is least disruptive to the family. The same option will be offered where families have emigrated to other countries. For these participants MRI scanning will not be performed.

In the extremely unlikely event that an unexpected structural brain abnormality is found on MRI a referral will be made to a Paediatric Neurologist and the GP will be notified. In the event that unexpected visual impairment is found in participants, referrals will be made to a Paediatric Eye specialist.

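### Movement ABC-2 is compared between arms only in mobile children, so the comparison is biased toward no effect if DRIFT makes more children mobile

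*Protocol*

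**What the plan says.** Section 6.3 lists "Assessment of motor ability using the Movement ABC-2 test in mobile children", alongside a full neurological assessment and a severity classification of cerebral palsy (Gross Motor Classification System). Neither of the latter two is limited to mobile children. The section does not define mobile.

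Section 7.4 opens with "Analysis will be performed by intention to treat" and later states: "For the secondary outcomes with continuous outcomes (eg Movement ABC), these will also be analysed using Students t-test". The sentence goes on to allow a transformation or a non-parametric method, but only if the scores are not normally distributed. It gives no score, rank or rule for a child who cannot take the test. The same section names functional motor impairment as a binary secondary outcome, tested by chi-square or Fisher's exact test.

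Section 4 makes improved sensorimotor ability secondary hypothesis (b), and section 4.2 lists sensorimotor disability as a secondary outcome. On the earlier follow-up, section 3.1.2 reports: "Sensorimotor disability remained substantial at 2 years: overall, 48% were unable to walk, and 20% were unable to communicate". It adds: "Severe sensorimotor disability was less common in the DRIFT group but without reaching statistical significance".

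**The concern.** Whether a child is mobile at school age is decided after randomisation and is part of what DRIFT is meant to improve. Restricting the t-test to mobile children therefore selects on the outcome domain under test. A child whom DRIFT moves from non-mobile to mobile joins the DRIFT mean with a low score, while a comparable control child stays non-mobile and drops out of the control mean. The control group that remains is the better part of its arm. The comparison is then weakest in the situation that the hypothesis describes.

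The protocol avoids this problem for cognition: section 6.1 provides a second test and a developmental quotient so that severely delayed children still receive a score. Movement ABC-2 has no such provision.

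At stake is a secondary motor result that could be read as showing little or no benefit when the restriction accounts for much of the shortfall.

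**Working it through.** **The plan's own figures (section 5.2).** An odds ratio of 0.17 on 59% gives 19.7%. The continuity-corrected formula then gives 28 per group, as stated. For a 1 SD difference with 30 per group, the normal approximation gives 97.2% and the noncentral t 96.8%, matching the stated 97%. The protocol gives no figure for Movement ABC-2.

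**Inputs.** From the protocol: 30 per arm, two-sided 5%, and 48% unable to walk at 2 years (both arms together). Assumed: normal latent motor ability, control N(0,1) and DRIFT N(δ,1); a common mobility cut-off c below which a child is not tested; δ = 0.72 SD; and 48%, 30% or 20% of controls non-mobile. The protocol gives neither a motor effect size nor a school-age non-mobile share.

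**Formula.** With a = c − μ, the mean among tested children is μ + φ(a)/[1 − Φ(a)].

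For 48% of controls non-mobile, c = −0.050:
- Control: 0.3984/0.52 = 0.766; tested 30 × 0.52 = 15.6.
- DRIFT: a = −0.770, so 22% are non-mobile and about 23.4 are tested; mean 0.72 + 0.2966/0.7794 = 1.100.
- Difference among tested children: 1.100 − 0.766 = 0.33 SD, or 46% of the true 0.72 SD.

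| Controls non-mobile | DRIFT non-mobile | Tested (control/DRIFT) | Mobile-only difference | Power, mobile-only t-test | Power, rank test, all children, non-mobile worst |
|---|---|---|---|---|---|
| 48% | 22% | 15.6 / 23.4 | 0.33 SD | about 28% | about 71% |
| 30% | 11% | 21.0 / 26.8 | 0.43 SD | about 46% | about 75% |
| 20% | 6% | 24.0 / 28.2 | 0.50 SD | about 57% | about 76% |

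Powers are from simulation; repeat runs of 6,000 trials agreed within about two percentage points. If every child could be scored, a t-test at 0.72 SD with 30 per arm would have 78% power.

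**No effect at all.** With δ = 0, the mobile-only t-test rejected in 4.9% to 5.7% of simulated trials. The restriction does not create false positives here.

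**No effect on mobility.** If the same share is mobile in each arm and mobile children differ by 0.72 of their own SD, the difference is not attenuated and only numbers are lost. Power is 49% with 15.6 per arm (48% non-mobile) and 69% with 24 per arm (20% non-mobile), against 78% with 30.

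**Other assumptions.** Taking 25% to 48% as the non-mobile share over both arms, and δ from 0.3 to 1.0 SD, the expected mobile-only difference is 38% to 56% of the true shift. For δ = 0.8 SD, power falls from 86% to between 48% and 24%.

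**An extreme case.** Suppose 42% of controls are mobile and DRIFT's only effect is to make a further share r mobile, with scores 1 SD below the other mobile children. The expected difference is −r/(0.42 + r): −0.19 SD at r = 10% and −0.42 SD at r = 30%. A benefit would then appear as harm.

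**The case against.** A reader might infer that a motor benefit of DRIFT would be hidden altogether. The protocol does not support that. The listed outcome is sensorimotor disability, for which Movement ABC-2 is one measure. The cerebral palsy classification and the binary functional motor impairment outcome have no mobility restriction. If functional motor impairment meant non-mobility (an assumption, since section 7.4 does not define it), the 48% v 22% scenario with 30 per arm gives z = (0.259 − 1.96 × 0.123)/0.1185 = 0.15. An uncorrected chi-square test then has about 56% power. This part of the objection stands, and it limits the point to the Movement ABC-2 comparison.

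The size also rests on assumptions. The 48% is an overall figure at 2 years, used in the table as a control-arm share at school age; that row implies about 35% non-mobile over both arms. The 0.72 SD has no source in the protocol, which reports only a non-significant difference favouring DRIFT in severe sensorimotor disability. This stands too, so the powers are illustrative.

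A reader might see a contradiction with the intention-to-treat statement. That statement does not promise a score on every instrument, and a test that includes ball skills and balance cannot be given to every child. The restriction on testing is a matter of feasibility; the point concerns the comparison built on it.

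It may be said that the rule for untestable children belongs in the statistical analysis plan, which is not at hand. A missing rule alone would be no finding. But section 7.4 already fixes the test and names this score as its example, and its non-parametric fallback depends on non-normality, not on untestable children.

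Finally, the argument might be stretched to imaging because of "For these participants MRI scanning will not be performed". Section 10.2 applies this where severe mobility or emotional problems make travel difficult, and to emigrated families; it does not exclude every child with such problems. Imaging is an aim but not a listed secondary outcome. It is not part of this point.

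**Conclusion.** The planned Movement ABC-2 t-test conditions on a post-randomisation motor state that DRIFT is hypothesised to improve. If DRIFT increases the share of mobile children, the comparison is biased toward no effect. Under the stated model, a true 0.72 SD benefit appears as 0.50 to 0.33 SD when 20% to 48% of controls are non-mobile, with roughly 20 to 40 percentage points less power than a worst-rank test of all children. If DRIFT leaves mobility unchanged, the cost is mainly sample size. The direction of the bias follows from the design; its size depends on a school-age non-mobile share and a motor effect that the protocol does not give. The point concerns one secondary measure, does not touch the primary outcome, and leaves the unrestricted motor measures intact. It is worth correcting because the remedy is cheap.

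**What to change.** In section 7.4, make the between-arm motor comparison one that includes every assessed child, by either route:

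- a rank test of Movement ABC-2 in which children untestable because of immobility are tied at the lowest rank; or
- an ordinal comparison of the Gross Motor Classification level already recorded under section 6.3.

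Present the mobile-only Movement ABC-2 mean difference as descriptive and conditional on mobility.

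The cost is analysis wording only; no new data are needed. The downside is that the motor result becomes a rank or ordinal effect, which is harder to interpret than a difference in mean score. The descriptive mean for mobile children partly makes up for that.

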6.4 Emotional and Behavioural Difficulties

The Strengths and Difficulties Questionnaire will be used. This is a brief behavioural screening tool for children and adolescents aged between 4 and 16 years of age. It comprises 25 items divided between 5 scales: emotional symptoms; conduct problems; hyperactivity/inattention; peer relationship problems; prosocial behaviour. There is a supplement which assesses impact including, chronicity, distress, social impairment and burden to others [16].

6.5 Quality of life, productivity, health, social care and other resource use

The Study Researcher will ask parents to complete the following questionnaires on behalf of their child.

- Two generic preference based measures of the child's health related quality of life: The HUI3, and the EQ-5D-5L proxy versions.
- A modified version of the Client Service Receipt Inventory (CSRI) Children's version [17] to assess parent/carer productivity (completed by both parents/guardians where applicable). The modified CSRI also assesses the child's use of hospital, and community based health services, social and supportive care, educational services in the past 12 months.

The Study Researcher will also extract information on hospital care from the hospital and primary care records since birth to estimate the cost of initial hospitalisation and subsequent readmissions.

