Reducing the rate of shunt insertion in these infants has been an important long-term objective in the management of IVH and PVHD. The large amount of blood and protein in the cerebrospinal fluid (CSF) combined with the small size and instability of the patient makes early ventriculoperitoneal shunt surgery impossible. Shunt implantation at the generally accepted weight threshold of 2kg, usually around term-age, is still associated with a higher infection and malfunction rate [3] [4].

Despite a number of different approaches to therapy, no intervention has been objectively shown to improve outcome. Repeated lumbar puncture, drugs to reduce cerebrospinal fluid (CSF) production and intraventricular injection of streptokinase have been tested in randomised trials with either no benefit or worse outcome in the intervention group.

Drainage, irrigation and fibrinolytic therapy (DRIFT) was developed as a surgical approach of reducing iron and pro-inflammatory cytokines from CSF and reducing pressure and distortion early [2]. The procedure involves insertion of right frontal and left occipital ventricular catheters under anaesthesia. Tissue plasminogen activator (TPA), a fibrinolytic, is injected intraventricularly at a dose that is insufficient to produce a systemic effect and this is left for approximately 8 hours. Under continuous intracranial pressure monitoring the ventricles are irrigated by artificial CSF through the frontal catheter. The occipital ventricular catheter is simultaneously connected to a sterile closed ventricular drainage system and the height of the drainage reservoir adjusted to increase or decrease drainage to maintain intracranial pressure below 7 mm Hg and net loss of 60–100 ml CSF/day. The drainage fluid initially looks like cola but gradually clears, at which point irrigation is stopped and the catheters removed. This commonly takes 72 hours but can be up to 7 days.

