4.2 Secondary Outcomes

- Cerebral visual function
- Sensorimotor disability
- Functional status
- Emotional/behavioural function
- Preference based measures of health related quality of life
- Costs of initial hospitalisation and treatment during the neonatal period (including emergency transportation, periods of intensive care, and readmissions based on hospital records in the UK cohort)
- Costs of subsequent health care in childhood (based on hospital records from the UK cohort)
- Health and social care costs and impact on family at age 11 (based on parent recall)

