5.1 Study Participants

Children previously enrolled in and randomised to the DRIFT trial in Bristol and Poland between 2003 and 2006.

Inclusion criteria of the DRIFT trial were:

- (1) IVH documented on ultrasound;
- (2) age no more than 28 days;
- (3) progressive dilation of the both lateral ventricles with each side:
 - (a) ventricular width 4 mm over the 97th centile;

(b) all of the following: anterior horn diagonal width 4 mm (1 mm over 97th centile), thalamo-occipital distance 26 mm (1 mm over 97th centile), and third ventricle width 3 mm (1 mm over 97th centile); or

(c) measurements above (a) or (b) on 1 side combined with obvious midline shift indicating a pressure effect.

Exclusion criteria were a prothrombin time of >20 seconds or accelerated partial thromboplastin time of >50 seconds or platelets <50000/mL.

The DRIFT study achieved a high level of loyalty from those recruited as 100% followup was obtained at 2 years with 97% of the survivors having the full Bayley Scales of Infant Development administered. All the families received a copy of the paper reporting the two year findings of the trial. The families with a child in the DRIFT trial will be invited to take part.

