9. ECONOMIC EVALUATION

The primary economic analysis will provide a preliminary assessment of the incremental NHS care costs of the DRIFT intervention compared to usual care based on data extracted from the hospital records combined with national and local unit cost data, discounted (at standard rates) over time. These data will be supplemented by a more detailed description of the broader impact of DRIFT on use of specialist rehabilitation services, education, informal care and family work patterns for children and their families at age 11. Due to the limited level of detail on quality of life and non-NHS resource use prior to age 11, we plan a cost consequence [18] analysis quantifying NHS resource use over the 11 year period and providing a more detailed snapshot of the broader perspective on economic (e.g. educational, rehabilitation costs, informal care, productivity) and quality of life impact at age 11. This will provide an estimate of whether the initial costs of DRIFT are counterbalanced by lower NHS secondary care costs during the first 11 years of life or lower societal costs and improved quality of life at age 11.

Modelling of long-term costs and outcomes: In secondary economic analysis, we will develop a decision tree and Markov model to estimate the cost-effectiveness (cost per quality adjusted life year [QALY]) of DRIFT compared to standard care from birth to age 18. The primary perspective will be NHS and personal social services in accordance with the NICE methods guide. However, in secondary analysis we will broaden the perspective to include education, parental expenses and lost productivity. The structure of the model will be similar to that outlined by Petrou and Khan using a Markov model to stratify cohorts of surviving children by the degree of disability (none, mild, moderate, severe) with an annual cycle length [13].

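### The DRIFT cost comparison starts at birth and leaves care before randomisation in the arm difference unadjusted, which adds avoidable noise but not bias

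*Protocol*

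**What the plan says.** Four parts of the protocol bear on this.

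- **Data (section 6.5, quality of life and resource use).** The researcher is to "extract information on hospital care from the hospital and primary care records since birth to estimate the cost of initial hospitalisation" and later readmissions.
- **Outcome (section 4.2).** The first cost outcome is "Costs of initial hospitalisation and treatment during the neonatal period", including transport and intensive care, for the UK cohort.
- **Analysis (section 9).** The primary economic analysis is a "preliminary assessment of the incremental NHS care costs of the DRIFT intervention compared to usual care based on data extracted from the hospital records". It asks whether the initial costs of DRIFT are "counterbalanced by lower NHS secondary care costs during the first 11 years of life". The secondary model also starts at birth and takes the cost of initial inpatient care up to discharge directly from trial data.
- **Entry (section 5.1).** The original trial required documented haemorrhage, progressive dilatation of the ventricles, and "age no more than 28 days".

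Nowhere is cost before randomisation separated from cost after it. Section 7.4 plans an unpaired t-test for continuous secondary outcomes, or a transformation or non-parametric method if they are not normal. It anticipates one sensitivity analysis that adjusts for the covariates of the original trial report, which it does not list. Section 9 states no covariate adjustment for costs.

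**The concern.** Care between birth and randomisation is a baseline quantity. Every child had some, because haemorrhage and progressive dilatation had to be documented first, and its amount varied with age at entry. DRIFT cannot have changed it. If the whole initial stay is compared between arms without adjustment, a chance difference in age at entry can appear as a cost or a saving of DRIFT.

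The stake is the precision and reading of the incremental NHS cost, the judgement on whether early costs are recovered later, and the model input for initial care. The clinical outcomes are not affected.

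**Working it through.** The protocol states no cost, cost SD, unit cost or age at randomisation, so it has no figure on this point to reproduce.

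**Inputs**
- UK children: 22 DRIFT, 23 control (section 5.2).
- Latest entry: 28 days (section 5.1).
- Irrigation time, as a yardstick only: "This commonly takes 72 hours but can be up to 7 days" (section 3.1).
- SD of age at entry: assumed, 3 to 8.1 days. The upper value is a flat spread over days 0–28: 28/√12 = 8.08.

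**Step 1: chance imbalance in pre-randomisation days.**
SE = SD × √(1/22 + 1/23) = SD × 0.298. The 95% chance range is ±1.96 × SE.

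| Assumed SD (days) | SE (days) | 95% chance range (days) | P(gap ≥ 3 days) | P(gap ≥ 7 days) |
|---|---|---|---|---|
| 3 | 0.89 | ±1.8 | 0.1% | <0.1% |
| 5 | 1.49 | ±2.9 | 4.4% | <0.1% |
| 7 | 2.09 | ±4.1 | 15% | 0.1% |
| 8.08 | 2.41 | ±4.7 | 21% | 0.4% |

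The expected gap is zero in every row.

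**Step 2: does the starting date matter after adjustment?**
Write total cost T = B + P, with B the cost before randomisation and P the cost after it. In a linear model with arm and B as covariates, replacing T by P = T − B lowers the coefficient of B by exactly 1 and leaves the arm coefficient unchanged. The adjusted difference is therefore the same from either date.

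**Step 3: effect on the SE.**
Costs are in day-costs (one average day of neonatal care). Age at entry is flat over days 0–28, with 4,000 simulated trials per setting. The SD in the first column is that of later cost in case (a) and of total cost in case (b).

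| SD (day-costs) | (a) Later cost independent of age at entry: from birth, unadjusted → adjusted | (b) Total stay fixed by maturity: from birth, unadjusted → adjusted |
|---|---|---|
| 10 | 3.88 → 3.05 (21% narrower) | 2.96 → 3.01 (1.7% wider) |
| 20 | 6.54 → 6.03 (8% narrower) | 6.03 → 6.12 (1.5% wider) |
| 30 | 9.25 → 9.04 (2% narrower) | 8.90 → 9.03 (1.5% wider) |

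The formula agrees for the first row of (a): √(8.08² + 10²) × 0.298 = 3.83 unadjusted, and 10 × 0.298 = 2.98 before the small loss for estimating a slope.

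**Step 4: moving the clock without adjusting.**
In case (b) with SD 10, T does not depend on B, so P = T − B has SD √(10² + 8.08²) = 12.86. The SE rises from 10 × 0.298 = 2.98 to 12.86 × 0.298 = 3.83. A simulation gave 2.97 to 3.79.

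**The case against.** The strongest reply is that nothing here is invalid. Randomisation gives a zero expected difference in earlier care. A total from birth is a proper description of cost to age 11. An ordinary confidence interval already covers chance imbalance, as does the model's probabilistic sensitivity analysis. Extraction since birth is also what the remedy needs. All of this stands, and it rules out calling the plan biased or the data collection wrong.

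The gain may also be small. Later cost covers intensive care, surgery and years of readmissions in a severely affected cohort, so its SD may well be large, and the gain is then a few per cent or nothing. This stands too.

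It can further be said that baseline adjustment belongs in an analysis plan that is not shown. That carries less weight. The protocol is not silent: it sets the starting point at birth, names the contrast an incremental cost of DRIFT, and gives an unadjusted test as the default for continuous secondary outcomes.

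A reader might infer that the imbalance could be as large as the cost of the DRIFT procedure. The documents do not support that. They give no procedure cost and no daily cost. Irrigation time leaves out catheter insertion under anaesthesia, the fibrinolytic and pressure monitoring. Even measured in days, a gap of 72 hours has a probability anywhere from 0.1% to 21% depending on the assumed SD, and a gap of 7 days has at most 0.4%. For the same reason no figure in pounds can be attached.

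**Conclusion.** The point holds as a modest matter of precision and interpretation. A known baseline quantity is left in the arm contrast without adjustment, and for 45 UK children it can move the difference by about ±1.8 to ±4.7 days of care by chance. That range rests on an assumed entry-age SD of 3 to 8.1 days; 28 days is a ceiling on entry age, not a typical value. Adjustment changes the SE by between about 20% narrower and 1–2% wider, depending on how variable later cost is and how it relates to earlier cost. Systematic bias is not shown, and costing from birth is not an error in itself. Minor priority.

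**What to change.** In section 9, and for the cost outcomes in section 4.2:

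- Split the extracted record at the randomisation date, and estimate the arm difference in mean cost with a linear adjustment for cost from birth to randomisation. Days by level of care may be used instead, but the result is then exactly independent of the starting date only if those days fully determine the earlier cost.
- Do not simply restart the clock at randomisation without this adjustment.
- In the model that starts at birth, add the pooled pre-randomisation cost equally to both arms.
- Keep from-birth totals by arm as description.

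The cost is wording plus one split of records already being extracted, assuming the randomisation dates are held in the trial database. No new patients or data sources are needed. The analysis loses one degree of freedom (more if days are entered by level of care), and in the unfavourable case the SE is 1–2% wider.
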